- Proportion of people on the various arms of treatment who develop ASEs or AEs at D7, D14, D28, and D35 from baseline (No severe adverse side effects are expected).
- Proportion of persons on the various arms of treatment who withdraw from study due to severe ASEs or AEs at D7, D14, D28, and D35 from baseline.
- Proportion of persons on the various arms of treatment who withdraw from study for reasons other than severe AEs at D7, D14, D28, and D35 from baseline.
- Proportion of persons with baseline discordant test results (False positive or false negative) between mRDT, rt PCR, and direct blood smear observation?

Exploratory endpoints

- Variability in level of decease in gametocyte load (rt-PCR Ct) in the various treatment arms at D7, D14, D28, and D35 from baseline.
- Variability in level of decease in gametocyte load (rt-PCR Ct) in the various treatment arms by gender, age, and trial entry parasite load, at D7, D14, D28, and D35 from baseline.
- Variability in attainment of absolute increase in Cycle threshold (Ct >20) in the various treatment arms at D7, D14, D28, and D35 from baseline.

- Variability in the proportion of participant who respect and complete prescribed treatment dosages (acceptability) in the various treatment arms.
- Variability in the proportion of participants who develop clinical symptoms in the various treatment arms at D7, D14, D28, and D35 from baseline.
- Variability in the proportion of participants who develop Severe ASEs in the various treatment arms at D7, D14, D28, and D35 from baseline (not expected).
- Variability in proportion of participants who withdraw from the study due to severe ASEs, in the various treatment arms, at D7, D14, D28, and D35 from baseline.
- Variability in proportion of participants who withdraw from the study for reasons other than severe AEs, in the various arms of treatment at D7, D14, D28, and D35 from baseline.

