This study will use the adapted Zelen design which has two steps in the consent process. At step one, informed individuals (students and workers) will be invited to participate in a screening and cohort survey on asymptomatic malaria, aimed at understanding the comportment of plasmodium parasite in asymptomatic plasmodium carriers over time. After informed consent is obtained during the first encounter (day 0), baseline assessments will be done and sociodemographic variables, clinical/medical history, physical assessment, prior medications information and participants' contact details will be recorded. Blood samples will be collected from each participant and examined for the presence of parasites (Gametocytes) using malaria rapid diagnostic test kit (mRDT). RDT positive samples will be re-examined with qPCR (quantitative polymerase chain reaction) and direct microscopy for confirmation. The qCPR will be repeated for negative samples and participants excluded if still negative. All qPCR positive samples will be further analyzed with rt PCR (real time polymerase chain reaction), for parasite quantification and specific stage identification, targeting specific parts of the gametocyte genes. Participants who fulfil the inclusion criteria will be randomly allocated in the 8 study arms in a 2:2:2: 2:2:2: 1:1 ratio for the 6 treatment and 2 control arms, respectively. In the second step, only participants from the intervention groups (TG1- to -TG7) will receive the information about the intervention and a second consent will be obtained from them. Treatment administration will be based on the allocation arm. The treatments will consist of Artemisia afra tea infusions for the 6 trial arms versus favored placebo infusions and desired regular tea for the 2 control arms. The participants who will decline to participate to an intervention will continue in the cohort study, as a control group on regular tea (TG 8).

Screening and recruitment: Screening will be done during at baseline visit (Day 0) in the health stations set up in the study sites. After informed consent is obtained, baseline assessments will be performed to obtain information on sociodemographic characteristics, clinical/medical history, physical assessment, prior medications, and participants' contact details. This will be followed by screening tests for presence of plasmodium parasites. Participants who fulfil the inclusion criteria will be enrolled in the study.

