Randomization: Prior to treatment, eligible participants will be randomly assigned into the 8 study arms. The randomization method will be a permuted block randomization, with a block size of either 14 or 28 at random, and with a two-to-one allocation ratio for each active arm against two different control arms (2:2:2:2:2:1:1).

Blinding: The participants in the intervention arms will be aware of their assignment to an intervention group but unaware of the treatment assigned to them. The site staff (investigators or observers) will be

aware of assignments to one control arm (regular tea group), but unaware of assignments in the other treatment arms.

Visits/assessment schedules: A total of five study visits will be effected, being one baseline visit on Day 0, and four follow-up visits on Day 7, 14, 28 and 35, from baseline. During the baseline visit plasmodium tests targeting specific parts of the gametocyte genes will be done to determine the participants' initial (baseline) parasite load, and during subsequent visits, follow up control tests (rtPCR and blood smear) will be done, and the gametocyte load recorded, alongside assessments for clinical symptoms and adverse sides effects (if any).

Endpoints The efficacy of each of the treatment dosage schedule will be evaluated on day 7,14,28 and 35 from baseline, based on response to treatment or reservoir elimination rate. Response to treatment will be indicated by an absolute increase in Cycle threshold (Ct >20), or a negative rt-PCR tests results (Ct >40). If the patient misses the follow-up visit, compliance will be noted in the completion worksheet (filled out at end of study) and the parasite load and adverse side effects noted during the last visit considered. No severe side adverse effects are expected from the treatment but since toxicity is always a concern in clinical trials involving humans, participants will be observed for any severe ASEs and withdrawal noted throughout the study duration.

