5.5 Randomization and Blinding Procedures

Randomization: After enrolment of eligible participants, a statistician will randomly assign them in the 8 study arms before treatment administration. The randomization method will be a permuted block randomization, with a block size of either 14 or 28 at random, and with a two-to-one allocation ratio for each active arm against two different control arms (2:2:2:2:2:2:1:1). The treatments will consist of *Artemisia afra* infusions for the 6 trial arms versus flavored placebo infusions and any desired regular tea for the 2 control arms.

Blinding: Neither the participants nor the site staff (investigators or observers) will know to which study arm the participants have been assigned.

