7.1 Solicited and Unsolicited Safety Measurements

Solicited side adverse effects: The term "side effects" refers to signs and symptoms occurring as unintended clinical effects of the treatment whether or not they are harmful (adverse).

Unsolicited Adverse Events: An adverse event (AE) is any undocumented untoward or unforeseen medical occurrence in a participant or clinical investigation participant administered a pharmaceutical product at any dose that does not necessarily have a known causal relationship with this treatment. This definition includes intercurrent illnesses or injuries and exacerbation of pre-existing conditions. In this study, no severe adverse side effects are expected from the treatment, given that Artemisia herbal teas have been used in communities for malaria prevention with no reported toxicity (29). However, since toxicity is always a major concern in clinical trials involving humans, each study participants will be monitored for adverse side effect or adverse events daily, throughout the study period (within 35 days of treatment administration) and where necessary adequate intervention will be provided. Treatment safety data will be collected continuously by the site staff during site and home visits and recorded in

the predefined visit worksheets at Visit Day 7, 14,28 and 35 (i.e, adverse effects). As a consistent method for collecting unsolicited ASE and AEs in this study, the participant will be asked a non-leading question such as: 'Have you acted differently or felt different in any way since receiving the treatment, or since the last study visit?' Occurrence of any adverse side effects or AEs visit within 35 days of treatment will be assessed by healthcare professional at site or home, meanwhile the site staff will continue contacting the participant daily until effects resolution.

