When an AE/ASE occurs, it is the responsibility of the investigator to review all documentation (e.g., hospital records, laboratory, and diagnostics reports) relative to the event. The investigator will then record all relevant information regarding an unsolicited AE/SAE on the eCRF or SAE Report screens as applicable. The investigator will attempt to establish a diagnosis pertaining to the event based on signs, symptoms, and/or other clinical information. In such cases, the diagnosis should be documented as the AE/ASE and not the individual signs/symptoms. The severity of AEs will be determined by the investigator and graded from Mild (Grade 1) to Death (Grade 5) based on the *Division of AIDS (DAIDS) Table for Grading the Severity of Adverse Events* (37).

The relationship of the study treatment to an AE will be determined by the investigator based on the following definitions:

- 1. Not Related: The AE is not related to an investigational treatment if there is evidence that clearly indicates an alternative explanation. If the participant has not received the treatment, the timing of the exposure to the treatment and the onset of the AE are not reasonably related in time, or other facts, evidence or arguments exist that reasonably suggest an alternative explanation, then the AE is not related.
- **2. Related:** The administration of the investigational treatment and AE are considered reasonably related in time and the AE could be explained by exposure to the investigational treatment or by other causes. The relationship of the study treatment to an unsolicited AE will be determined by the investigator.

The causality assessment is made based on the available information at the reporting time point and assessment of causality can change according to follow-up information.

The actions taken in response to an unsolicited AE will be coded as shown below. One or more of these actions may be selected:

- 0 No action taken
- 1 Study treatment temporarily interrupted
- 2 Study treatment permanently discontinued due to this adverse event
- 3 Concomitant medication taken
- 4 non-drug therapy given
- 5 Physician visit
- 6 Hospitalization/prolonged hospitalization

Outcome of any unsolicited AE reported during the study period will be assessed as:
□ Recovered/resolved
☐ Recovering/resolving
☐ Not recovered/not resolved
☐ Recovered with sequelae/resolved with sequelae
☐ Fatal (SAEs only)

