7.1.2 Methods for Assessing and Recording AEs and Serious AEs (SAEs)

relationship.

The period of observation for AEs extends from the time the participant signs informed consent until he or she completes the final study visit (Visit 5) or terminates the study early. AEs occurring after the informed consent form is signed but prior to receiving study treatment will be documented as an adverse

event. However, AEs occurring prior to receipt of any treatment will be considered separately from "treatment emergent" AEs.

All AEs meeting criteria for reporting, regardless of severity, will be monitored by the investigator until resolution or stabilization. All participants experiencing AEs - whether considered associated with the use of the study treatment or not - must be monitored until symptoms subside and any abnormal laboratory values have returned to baseline, or until there is a satisfactory explanation for the changes observed, or until death, in which case a full pathologist's report should be supplied, if possible. All findings must be appropriately reported on the eCRF, which is part of the Investigator's Site File.

All severe AEs must be reported within 24 hours of the site becoming aware of the event by telephone or email to Project coordinator/Sponsor. If the investigator does not have all information regarding a SAE, the SAE should still be reported within 24 hours. Once additional relevant information is received, the SAE form should be updated within 24 hours, including an assessment of causality. Any medication or other therapeutic measures used to treat the AE will be recorded on the appropriate eCRF(s) in addition to the outcome of the AE.

After receipt of the initial report, representatives of sponsor will contact the investigator if it is necessary to obtain further information for assessment of the event.

All SAEs must be reported by the investigator to his/her corresponding EC/IRB or applicable regulatory authorities in accordance with institutional policy/regulatory requirements and adequate documentation of this notification must be provided to the sponsor.

The Sponsor and its designee must also comply with the applicable regulatory requirement(s) related to the reporting of unexpected serious and non-serious adverse drug reactions (also referred to as "SUSARs") to the regulatory authority(ies) and the IRB/EC. If a SUSAR or other

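### Attributed harms (side effects, related adverse events) are not comparable with the regular-tea arm TG8: the attribution rules are undefined for it, and assessors may know the assignment

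*Protocol*

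**What the plan says.** **Attribution.** Section 7.1 says that the term side effects "refers to signs and symptoms occurring as unintended clinical effects of the treatment". Under its causality rules, a related AE needs exposure to the investigational treatment, and the conditions for calling an AE not related begin "If the participant has not received the treatment, the timing of the exposure to the treatment". Section 7.1.1 treats an SAE in the same way when the treatment has not been consumed.

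**What TG8 receives and is told.** Section 6.1 describes regular tea as whatever tea the participant usually drinks. Section 3 (Study description) states that "only participants from the intervention groups (TG1- to -TG7) will receive the information about the intervention", so people randomised to TG8 are not told of an intervention.

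**Who knows the TG8 assignment.** The Blinding paragraph of section 3 says site staff, investigators included, are "aware of assignments to one control arm (regular tea group") but not of the other arms. Section 5.5 says "Neither the participants nor the site staff (investigators or observers) will know to which study" arm participants belong.

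**Elicitation and timing.** The example question in section 7.1 asks whether the participant has "felt different in any way since receiving the treatment, or since the last study visit". Section 7.1.2 adds that "AEs occurring prior to receipt of any treatment will be considered separately from" treatment-emergent ones.

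**Where attributed harms are used.** Secondary objective 3 (section 2.3.2) and the synopsis safety outcome are worded as ASEs; the matching outcome in section 2.3.2 is abbreviated as SAEs. Two exploratory endpoints, severe ASEs and withdrawal for severe ASEs, count ASEs only. The main harm endpoint is wider: "Proportion of people on the various arms of treatment who develop ASEs or AEs at D7, D14" and later visits.

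**The concern.** An ASE or a related AE is a judgement that the treatment caused the event. In TG1-TG7 the assessor can make that judgement for any complaint whose timing fits. In TG8 the assessor may know that the participant is drinking their own habitual tea, and the rules can then be read as requiring the answer no. The same headache would count as a side effect in one arm and not in the other.

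At stake is the safety part of the trial's hypothesis, wherever it rests on ASE-only measures set beside TG8 or beside both controls combined. TG8 is 8 of the 16 planned controls. A harmless infusion could appear to cause side effects through the attribution rule alone.

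**Working it through.** **1. Arm sizes.** Section 8.1 gives 8 per active arm and 4 per control arm at each of two sites.

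- Per site: 6 × 8 + 2 × 4 = 56. Total: 2 × 56 = 112. Both match the protocol.
- Active: 2 × 48 = 96. TG7: 2 × 4 = 8. TG8: 2 × 4 = 8.

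**2. Does treatment include regular tea?** The text supports both answers.

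| Regular tea is treatment | Regular tea is not treatment |
|---|---|
| Section 3 lists TG8 as a treatment group receiving a tea placebo for 7 days | Section 7.1 requires the investigational treatment for a related AE |
| Sections 3 and 5.5 name it when saying what the treatments consist of | Section 3 limits the intervention groups to TG1-TG7 |
| Table 5 lists it among the formulations | Section 6.1 makes it the participant's usual tea, so not a new exposure |

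Section 8.2.4 admits to the Safety Population only those who received a study treatment, so TG8's membership depends on the same unanswered question.

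**3. Size under the literal reading.** Let p be the background complaint rate over 35 days, equal in all arms (no true effect), and q the share attributed to treatment where attribution is possible. Attribution in TG8 is set to 0. Both p and q are assumptions.

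- Against TG8: p·q − 0 = p·q
- Against TG7 and TG8 pooled: p·q − (8·p·q + 8·0)/16 = p·q/2
- Against TG7: p·q − p·q = 0
- All-cause AEs, any arm: p − p = 0

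| p | q | vs TG8 (points) | vs pooled (points) | vs TG7 | all-cause |
|---|---|---|---|---|---|
| 10% | 0.5 | 5 | 2.5 | 0 | 0 |
| 10% | 1.0 | 10 | 5 | 0 | 0 |
| 20% | 0.5 | 10 | 5 | 0 | 0 |
| 20% | 1.0 | 20 | 10 | 0 | 0 |
| 30% | 0.5 | 15 | 7.5 | 0 | 0 |
| 30% | 1.0 | 30 | 15 | 0 | 0 |

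**4. What 8 people can show.** The chance of no event among 8 is (1 − p)^8: 43% at p = 10%, 17% at 20%, 6% at 30%. The exact 95% upper limit for 0 of 8 is 1 − 0.025^(1/8) = 36.9%. Fisher's exact test of 29/96 against 0/8, about the most extreme row, gives p = 0.10. The distortion would therefore appear in tables by arm more than as a significant test.

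**The case against.** A reader might infer that harms are not collected in TG8, that its harm count is zero by construction, or that the whole active-versus-control comparison is biased. The documents support none of these.

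- **Collection covers TG8.** AEs are observed from consent to Visit 5 (section 7.1.2), recorded at every follow-up visit (Table 4), and each arm has its own observer (section 6.2). The prompt is only an example, and its second half can be answered by anyone.
- **AEs need no causal link.** Section 7.1 includes intercurrent illness, so a TG8 headache counts towards the AE part of the main harm endpoint.
- **A TG8 zero is not fixed.** On the broader reading in step 2, TG8 has a 7-day course that could be attributed. Read very narrowly, the investigational treatment would exclude TG7's placebo too.
- **TG7 is a sound comparator.** It receives the intervention information, and both blinding statements keep staff unaware of it, so the rules fall on it as on the active arms.
- **No attributed-harm test against TG8 is specified.** Objective 3 is framed by concentration, frequency, duration and flavour. Related and treatment-emergent AEs are not listed endpoints.

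All of this stands and sets the limits of the point. It does not remove the ASE-only measures, which are to be shown by arm with TG8 among them. Nor does it settle what treatment means for TG8 or which blinding statement holds.

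**Conclusion.** The point holds for attributed harms only. ASEs, severe ASEs and related AEs in TG8 cannot be set against those in the other arms, because the protocol does not say whether regular tea is the treatment to which an event may be attributed, and it contradicts itself on whether the assessor knows the arm. The measures affected are secondary objective 3, the synopsis safety outcome and the severe-ASE endpoints. All-cause AE collection, the AE component of the main harm endpoint and comparisons with TG7 are not affected.

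The false excess of 5-30 points against TG8 (2.5-15 against pooled controls) is an illustration. It needs the literal reading, with no attribution in TG8, and assumed rates of p = 10-30% and q = 50-100%; the protocol gives neither. On the broader reading it shrinks or vanishes, but a blinding contradiction would remain. With 8 people, TG8 could not support a firm conclusion on harms in any case.

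**What to change.** 1. Make the eight-arm harm comparison on all-cause AEs with onset from randomisation (Day 0) to Day 35, whatever the attribution.
2. Compare ASEs, severe ASEs and related AEs only among TG1-TG7, with TG7 as control, and leave TG8 out of those rates.
3. Use one neutral prompt in every arm, anchored on *since the last contact*, without reference to receiving a treatment.
4. State in sections 7.1, 7.1.1 and 8.2.4 whether regular tea counts as study treatment, so that TG8's place in the Safety Population is fixed. Whatever the answer, the population for item 1 must include TG8.
5. Reconcile the Blinding paragraph of section 3 with section 5.5 on who knows TG8 assignments.

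The cost is wording in sections 2.3.2, 3 or 5.5, 7.1, 7.1.1 and 8.2.4, and one line on the visit worksheet. No visits, staff or participants are added, since the AE data are already collected. The downside is that attributed comparisons then rest on 8 TG7 participants.

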7.1.1 Serious Adverse Events
A serious adverse event (SAE) is defined as any untoward medical occurrence that at any dose results
in one or more of the following:
- Death.
- Is life-threatening (i.e., the participant was, in the opinion of the investigator, at immediate risk
of death from the event as it occurred); it does not refer to an event which hypothetically might have
caused death if it were more severe.
- Required or prolonged hospitalization.
- Persistent or significant disability/incapacity (i.e., the event causes a substantial disruption of a
person's ability to conduct normal life functions).
- An important and significant medical event that may not be immediately life threatening or resulting
in death or hospitalization but, based upon appropriate medical judgment, may jeopardize the
participant, or may require intervention to prevent one of the other outcomes listed above.
Adverse events which do not fall into these categories are defined as non-serious .
All Severe AEs will be evaluated by the investigator for relationship of the event to study treatment.
The relationship of the study treatment to an SAE will be determined by the investigator based on the
following definitions:
$\hfill \square$ Related/suspected : the SAE is judged by the investigator to be related to the trial treatment ;
$\ \square$ Not Related : the SAE is not related the treatment has not yet been consumed, \mathbf{or} the occurrence of
the SAE is not reasonably related in time, \mathbf{or} the SAE is considered unlikely to be related to use
consumption of the treatment i.e., there are no facts (evidence) or arguments to suggest a causal

7.1.2 Methods for Assessing and Recording AEs and Serious AEs (SAEs)

relationship.

The period of observation for AEs extends from the time the participant signs informed consent until he or she completes the final study visit (Visit 5) or terminates the study early. AEs occurring after the informed consent form is signed but prior to receiving study treatment will be documented as an adverse

event. However, AEs occurring prior to receipt of any treatment will be considered separately from "treatment emergent" AEs.

All AEs meeting criteria for reporting, regardless of severity, will be monitored by the investigator until resolution or stabilization. All participants experiencing AEs - whether considered associated with the use of the study treatment or not - must be monitored until symptoms subside and any abnormal laboratory values have returned to baseline, or until there is a satisfactory explanation for the changes observed, or until death, in which case a full pathologist's report should be supplied, if possible. All findings must be appropriately reported on the eCRF, which is part of the Investigator's Site File.

All severe AEs must be reported within 24 hours of the site becoming aware of the event by telephone or email to Project coordinator/Sponsor. If the investigator does not have all information regarding a SAE, the SAE should still be reported within 24 hours. Once additional relevant information is received, the SAE form should be updated within 24 hours, including an assessment of causality. Any medication or other therapeutic measures used to treat the AE will be recorded on the appropriate eCRF(s) in addition to the outcome of the AE.

After receipt of the initial report, representatives of sponsor will contact the investigator if it is necessary to obtain further information for assessment of the event.

All SAEs must be reported by the investigator to his/her corresponding EC/IRB or applicable regulatory authorities in accordance with institutional policy/regulatory requirements and adequate documentation of this notification must be provided to the sponsor.

The Sponsor and its designee must also comply with the applicable regulatory requirement(s) related to the reporting of unexpected serious and non-serious adverse drug reactions (also referred to as "SUSARs") to the regulatory authority(ies) and the IRB/EC. If a SUSAR or other

safety signal relating to use of any of the study treatments is reported to the sponsor or its designee, the sponsor will communicate the information to the investigator and the investigator will be responsible for submitting this information to the EC/IRB and other relevant authorities.

